10.1.9. Retention of Records

Records and documents pertaining to the conduct of this study and the distribution of study records including eCRFs, ICFs, laboratory test results, safety reporting forms, source documents, medication inventory records, and adequate documentation of relevant correspondences (eg, letters, meeting minutes, telephone calls reports) must be kept on file by the PI for a minimum of 2 years after notification by the Sponsor that a marketing application has been approved for LASN01. If no application is filed or approved, these records must be kept for 3 years after the investigation has been discontinued and the United States FDA and applicable foreign authorities have been notified. The Sponsor will notify the PI of these events. No study records should be destroyed without prior authorization from the Sponsor.

10.1.10. Dissemination of Clinical Study Data

After the end of study, a CSR will be written and submitted to relevant IRB and regulatory authorities in accordance with local requirements.

At a patient's request, medical information may be given to his or her personal physician or other appropriate medical personnel responsible for his or her welfare.

10.1.11. Study and Site Start and Closure

The Sponsor requires the following data and materials before a study can be considered complete or terminated:

- Laboratory findings, clinical data, and all special test results from Screening visit throughout the study until the EOS visit
- eCRFs (including data queries) properly completed by appropriate study personnel and signed and dated by the PI
- Copies of complete drug accountability records (drug inventory log and an inventory of returned or destroyed clinical material)
- Copies of protocol amendments and concerned regulatory authority and/or ethics committee approval and notification, if appropriate
- A summary of the study prepared by the PI (a summary letter is acceptable from the concerned regulatory authority and/or ethics committee)

10.1.11.1. Early Study or Site Termination

The study or study site may be terminated before study completion at the discretion of the Sponsor if any of the following criteria are met:

- Medical or ethical reasons affecting the continued performance of the study
- Difficulties in the recruitment of patients
- Administrative reasons, including, but not limited to, cancelation of IP development

Throughout the study, the PI is to make a reasonable effort to maintain the enrollment rate that was agreed upon with the Sponsor. The PI will also make a reasonable effort to enroll appropriate patients.

10.1.12. Publication Policy

This clinical study will be registered on <https://clinicaltrials.gov/> or other registries by the Sponsor as required by local regulations, in keeping with the registration policy of the [International Committee of Medical Journal Editors \(2021\)](#).

Publication of study results may be addressed in the Clinical Trial Agreement. The Sponsor may publish the results of this study following completion of data analysis. The data generated in this clinical study are the exclusive property of the Sponsor and are confidential.

10.2. Appendix 2: Clinical Laboratory Tests

Hematology Hematocrit Hemoglobin Platelet count Red blood cell count Total and differential leukocyte count Reticulocyte count	Serum Chemistry Alanine aminotransferase Albumin Alkaline phosphatase Aspartate aminotransferase Bicarbonate Bilirubin (total, indirect, and direct) Urea Calcium Creatine kinase Creatinine ^b Chloride Gamma glutamyl transferase Glucose Lactate dehydrogenase Potassium Sodium Total protein Hemoglobin A1c Thyroid stimulating hormone (TSH) Triiodothyronine (T3) Thyroxine (free T4) Thyroid stimulating immunoglobulin (TSI)	Urine Drug Screen Amphetamines Barbiturates Benzodiazepines Cannabinoids Cocaine Methylenedioxymethamphetamine Methadone Opiates/opioids Phencyclidine Cotinine test
Urinalysis Appearance Bilirubin Blood ^a Color Glucose Ketones pH Protein ^a Leukocyte esterase Nitrite Specific gravity Urobilinogen ^c		Additional Tests Follicle-stimulating hormone as applicable Hepatitis B virus surface antigen Hepatitis C virus antibody Human immunodeficiency virus antibody (HIV-1 and HIV-2) Severe acute respiratory syndrome coronavirus 2 by PCR antibody test ^c Serum or urine pregnancy (for females of child-bearing potential only) ^d
Coagulation Tests Activated partial thromboplastin time Prothrombin time International normalized ratio		

- If urinalysis is positive for protein or blood cells, a microscopic examination (for red blood cells, white blood cells, bacteria, casts, and epithelial cells) will be performed.
- Creatinine clearance will be calculated using the Cockcroft-Gault formula.
- To be conducted locally if applicable per the site's standard practice.
- To be considered not of child-bearing potential, a female must either be surgically sterile for ≥ 6 months (ie, hysterectomy, bilateral salpingectomy, bilateral oophorectomy), or postmenopausal (no menses ≥ 12 months without an alternative medical cause and follicle-stimulating hormone in menopausal range).

10.3. Appendix 3: AEs and SAEs: Definitions and Procedures for Recording, Evaluating, Follow Up, and Reporting

10.3.1. Definition of AE

An AE means any untoward medical occurrence associated with the use of a drug in humans, whether or not considered study drug related. An AE (also referred to as an adverse experience) can be any unfavorable and unintended sign (eg, an abnormal laboratory finding), symptom, or disease temporally associated with the use of a drug and does not imply any judgment about causality. An AE can arise with any use of the study drug (eg, off-label use, use in combination with another drug) and with any route of administration, formulation, or dose, including an overdose. The following are not AEs:

- Any non-serious AE that occurs after signing the ICF, but before dosing, unless related to a study procedure
- Any clinically significant abnormal laboratory findings or other abnormal safety assessments that are associated with the underlying disease, unless judged by the PI (or designee) to be more severe than expected for the patient's condition
- The disease/disorder being studied or expected progression, signs, or symptoms of the disease/disorder being studied, unless more severe than expected for the patient's condition)
- Medical or surgical procedure (eg, endoscopy, appendectomy): the condition that leads to the procedure is the AE
- Situations in which an untoward medical occurrence did not occur (eg, social and/or convenience admission to a hospital)
- Anticipated day-to-day fluctuations of pre-existing disease(s) or condition(s) present or detected at the start of the study that do not worsen
- Clinical changes consistent with progression of the underlying disease (ie, TED).

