7.2. Early Discontinuation of Study Intervention

Patients who prematurely discontinue study drug should still remain on study for scheduled visits and assessments and every effort should be made to obtain all protocol-specified assessments to avoid losing data that is needed to evaluate safety and efficacy. The assessments for primary, secondary, and exploratory endpoints, including the MRI and facial photography, should be completed within 30 days of the study drug discontinuation. The reason for premature discontinuation of study drug administration should be recorded on the appropriate page(s) of the eCRF.

Study drug must be discontinued in case of progressing disease posing an unacceptable risk to the patient that requires immediate treatment. In such cases, the PI should contact the Sponsor and the PI and the Sponsor Medical Monitor will discuss and determine whether the patient should continue in the study.

Reasons for withdrawal from study drug may include, but are not limited to:

- Withdrawal of consent
- An AE, which, in the opinion of the PI (or designee), warrants the patient's discontinuation of study drug infusion; in the event of study drug withdrawal due to the occurrence of an AE, the Medical Monitor must be notified within 24 hours
- Non-compliance with study drug administration or other protocol procedures
- Prohibited concomitant medication
- Physician decision
- Pregnancy
- Study termination

A patient who is withdrawn from study drug, or patients who are randomized, but not dosed, for reasons not related to study drug or progression of TED may be replaced at the discretion of the Sponsor.

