7.4. Criteria for Discontinuation of Study

In the event of a negative change to the risk/benefit assessment, study enrollment will be suspended and the protocol revised as needed to ensure patient safety. Enrollment will be suspended if ANY of the criteria listed below are met. If the study is suspended due to meeting any of the criteria below, it may only be restarted after review and agreement by SRC and Sponsor. In countries for which restart of enrollment is considered a substantial amendment, enrollment will only be restarted once the relevant health authorities approve the revised protocol.

- The occurrence of an SAE or severe AE, assessed as related to the study drug, of similar origin in ≥ 3 patients
- If unacceptable risks to study patients are identified
- If, in the Sponsor's judgment, there are no further benefits to be achieved from the study

In the event that the clinical development of the study drug is discontinued, the Sponsor shall inform the PI/institution and regulatory authorities.

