8.2. Safety Assessments

An SRC will be formed for periodic reviews of safety and available PK and PD data. For the randomized, double-blind treatment arms, the SRC will review masked data. The SRC will be minimally composed of the Medical Monitor, at least 1 study PI, and at least 1 independent member with expertise in the treatment of TED. In cases where the SRC determines that an unexpected or critical finding requires expert opinion or access to unmasked data, the SRC may refer the question to at least 3 independent experts selected by the Sponsor, including the SRC

Chair, to assess the situation by reviewing necessary unmasked data and provide recommendation back to the SRC. The SRC charter will describe the committee member structure and details for the conduct and safety review meetings.

Safety will be assessed throughout the study by examination of visual acuity, visual fields, and color defects; TEAEs; changes in concomitant medications; and changes from Baseline in clinical laboratory evaluations, vital signs, 12-lead ECGs, ophthalmic assessments, and physical examinations. Safety assessments by visit are listed in [Table 1](#). Safety monitoring ([Section 10.1.6.1](#)) and reporting ([Section 8.3](#)) are summarized. Additional safety assessments may occur at the discretion of the PI (or designee).

Any ongoing study drug-related SAEs or severe TEAEs present at the time of study termination will be followed until resolved or until the event stabilizes and the overall clinical outcome has been ascertained. All other TEAEs considered related to study drug and SAEs considered not related to study drug will be followed for 30 days after the EOS/ET visit or after the last dose of study drug, whichever is later.

In the event of unexplained, treatment-emergent, clinically significant, abnormal laboratory values or clinically significant changes in laboratory values from Baseline, the laboratory tests should be repeated immediately and followed until the values have returned to within the reference range or to Baseline.

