6.4 Adjustments for Multiplicity

As this is an early-phase proof-of-concept study, there is no strong control of the family-wise error rate ($\alpha = 0.1$), and there are no multiplicity adjustments for the primary or secondary efficacy endpoints.

7. Disposition of Patients

Patient disposition will be presented in terms of the number of patients who were randomized to masked study medication [REDACTED], with subcategories of treated patients. The number and percentages of patients will be summarized for the analysis populations including the Efficacy, Safety, PK, and PD Populations. Number and percentage of patients who completed the study and discontinued from the study will be summarized. Patients who are not discontinued from the study will be considered study completers. Number and percentage of patients who completed treatment and discontinued the treatments early will be summarized. Completing treatment will be based on the patients' most recent consented protocol version. Disposition will be summarized by treatment arm, including LASN01 300 mg, LASN01 600 mg, placebo, [REDACTED], and overall for all patients. Percentages will be calculated using randomized (or enrolled patients) as the denominator unless otherwise specified.

The reasons for premature study discontinuation and treatment discontinuation will be summarized by treatment arm and overall for all discontinued patients. Percentages will be calculated using discontinued patients as the denominator. The reasons for study discontinuation that will be summarized include: Death, Lost to Follow-up, Physician Decision, Protocol non-compliance with protocol procedures, Study Termination, Withdrawal of Consent, and Other. The reasons for treatment discontinuation that will be

CONFIDENTIAL

The contents of this document are confidential to [REDACTED]
Unauthorized use, disclosure, or reproduction is strictly prohibited.

summarized include: Adverse Event, Non-compliance with study drug administration or other protocol procedures, Physician Decision, Pregnancy, Prohibited Concomitant Medication, Study Termination, Withdrawal of Consent, and Other. A patient listing will be provided that includes the date of and reason for premature study and treatment discontinuation.

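### Protocol Section 10.3.1 contradicts itself on TED progression, so whether unexpectedly severe worsening is recorded as an AE or SAE depends on which bullet a site applies

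*Protocol*

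**What the plan says.** Section 10.3.1 of the protocol defines an AE and then gives seven kinds of occurrence that are not AEs. Three of them touch the disease under study.

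- The second bullet removes abnormal laboratory and other safety findings linked to the underlying disease, "unless judged by the PI (or designee) to be more severe than expected for the patient's condition".
- The third bullet removes "The disease/disorder being studied or expected progression, signs, or symptoms of the disease/disorder being studied, unless more severe than expected for the patient's condition".
- The last bullet removes "Clinical changes consistent with progression of the underlying disease (ie, TED", with nothing after it that restores severe cases.

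Other sections build on this list. Section 10.3.2 defines an SAE as an AE or suspected adverse reaction with a serious outcome, and Section 10.3.1.1 defines a suspected adverse reaction as a kind of AE. The count criterion for suspending enrollment in Section 7.4 is "The occurrence of an SAE or severe AE, assessed as related to the study drug", of similar origin, in at least 3 patients. Section 7.2 deals separately with dangerous progression: "Study drug must be discontinued in case of progressing disease posing an unacceptable risk to the patient that requires immediate treatment". It then asks the PI to contact the Sponsor.

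**The concern.** Two bullets in one list give opposite answers for the cases that matter most. Expected TED progression is excluded by both. Worsening beyond expectation stays reportable under the third bullet and is excluded under the last. Nothing in the protocol ranks them.

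The stakes are in the safety comparison. Protocol Section 2.3.1 says the risk profile of LASN01 is not yet fully characterized and that data on circulating IL-11 after withdrawal are pending. Drug-related or withdrawal-related worsening of TED is therefore an open question. A masked investigator looking at one patient cannot separate it from natural progression; a comparison between arms can. If some sites label such worsening as progression and record nothing, while others record an AE, the TEAE data reflect site reading habits as well as treatment.

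**Working it through.** The plan states no figure on this point, so the check is a comparison of texts.

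**Step 1: how the list works.** The items are separate entries under one lead-in. Meeting any one of them, read literally, is enough to exclude an event.

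**Step 2: where the bullets differ.**

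| TED worsening | Third bullet | Last bullet |
|---|---|---|
| Expected for the patient | Not an AE | Not an AE |
| Unexpectedly severe | Can be an AE | Not an AE |

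The last bullet changes the outcome only in the second row. For TED worsening, its sole added effect is to take out what the third bullet keeps in.

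**Step 3: what follows from each reading, for unexpectedly severe worsening.**

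| Step | Site applies third bullet | Site applies last bullet |
|---|---|---|
| AE record (10.3.3.1) | Yes | No |
| Causality assessment (10.3.3.3, Table 6) | Yes | No |
| SAE if a 10.3.2 criterion is met | Yes | No, because both routes need an AE |
| 24-hour report if serious (10.3.4) | Yes | No |
| TEAE tables (SAP 12.1) | Yes | No, because only TEAEs are summarized |
| Count under 7.4 | Only if serious or severe, and assessed as related | No |

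**Step 4: order of judgments.** Table 6 treats an AE as related unless the criteria for not related are met. The last bullet acts before that default is reached. It lets an attribution to TED decide whether the event is an AE at all, although the same section says that calling something an AE implies no view on cause.

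**Step 5: size.** The documents give no rate of severe TED worsening, so no expected number can be calculated. What can be stated is the weight of a single patient. Planned arms are 8 each (protocol Table 2), so one patient recorded or not recorded moves that arm's incidence of the event by 1/8 = 12.5 percentage points. If that event would have been assessed as related and met the other conditions of 7.4, it is also one of the 3 patients that the criterion needs.

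**The case against.** The strongest reply is that the documents, read as a whole, favor recording these events, and much of that stands.

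- The second and third bullets both restore unexpectedly severe findings. Vision tests are safety assessments ("Safety will be assessed throughout the study by examination of visual acuity, visual fields, and color defects", Section 8.2), so they fall under the second bullet's exception.
- Patients enter with disease that does not threaten sight, and known optic neuropathy or compression is an exclusion. Sight-threatening change can reasonably be judged beyond expectation.
- Table 6 names underlying disease as a possible cause of an AE classed as not related, which presupposes that such AEs are recorded.
- The primary safety endpoint also covers ophthalmic assessments and concomitant medications. SAP Sections 12.2, 12.3, 12.5 and 12.7 summarize 15-letter acuity loss, visual fields, slit-lamp findings (cornea included) and fundoscopy (optic nerve included) by arm, whatever the AE status.
- Section 7.2 brings dangerous progression to the Sponsor, and all deaths are reportable (10.3.2.1).

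Three stronger readings are tempting but not supported.

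1. A reader might infer that sight-threatening worsening can never be an AE or SAE. That takes the last bullet as overriding the others, and no text says so.
2. A reader might infer that the last bullet alone keeps three such events from triggering Section 7.4. The count takes only events assessed as drug-related, so worsening attributed to TED would not count under either bullet. Section 7.4 also has a criterion without a count, for unacceptable risks. The real loss is narrower: an event that might have been assessed as related is never assessed.
3. A reader might infer that stops for progression are hidden because the SAP's discontinuation reasons are "Adverse Event, Non-compliance with study drug administration or other protocol procedures, Physician Decision, Pregnancy, Prohibited Concomitant Medication, Study Termination, Withdrawal of Consent, and Other" (SAP Section 7). The Section 7.2 list is expressly open-ended, and the SAP lists the reason for each patient.

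What the reply does not answer is the conflict itself. Tables by visit trigger no expedited report. Section 7.2 covers only progression that needs immediate treatment and sets no 24-hour limit for reporting it.

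**Conclusion.** The contradiction is real and should be removed. As written, the recording of unexpectedly severe TED worsening depends on which bullet a site follows. That choice carries through to causality assessment, SAE status, 24-hour reporting, the TEAE tables and, for events assessed as related, the Section 7.4 count.

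The conclusion rests on the wording alone. It assumes that sites may read the list literally and that no study manual or training settles the order of the bullets; the documents show no such rule. It does not claim that any event was missed, and its effect on this trial cannot be sized from the documents. The ophthalmic tables keep a comparison between arms for vision and eye structure, so the weakness lies in AE and SAE reporting and not in safety data as a whole.

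**What to change.** **Wording.** Delete the last bullet of Section 10.3.1, or give it the third bullet's exception. Add one sentence: TED worsening that is more severe than expected is assessed as an AE and, if it meets a Section 10.3.2 criterion, as an SAE. This concerns reporting only and changes no treatment rule.

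**Retrospective check.** SAP Sections 1 and 16 record early termination, so a change of wording alone would do little for this trial. Review recorded TED worsening, Section 7.2 contacts with the Sponsor, and treatment stops filed as Physician Decision or Other, for events that were not reported. If the database is not yet locked, people still masked to arm should do this; SAP Section 16 says the sponsor's clinical team was unmasked. State in the study report that the definition was ambiguous and how it was applied.

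**Optional.** A progression category among the discontinuation reasons would make such stops easier to tabulate, but it is not needed to resolve the conflict.

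**Cost.** One bullet, one sentence and a limited data review, with a few more AE or SAE reports. The expected course of TED stays excluded by the third bullet, and ordinary fluctuation by the separate bullet on day-to-day variation.

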10.3.1.1. Definition of Suspected Adverse Reaction

A suspected adverse reaction is any AE for which there is a reasonable possibility that the drug caused the AE. For the purposes of IND safety reporting, "reasonable possibility" means there is evidence to suggest a causal relationship between the drug and the AE. Suspected adverse reaction implies a lesser degree of certainty about causality than adverse reaction, which means any AE caused by a drug.

10.3.1.2. Definition of Life-Threatening AE or Life-Threatening Suspected Adverse Reaction

An AE or suspected adverse reaction is considered "life threatening" if, in the view of either the PI (or designee) or Sponsor, its occurrence places the patient or patient at immediate risk of death. It does not include an AE or suspected adverse reaction that, had it occurred in a more severe form, might have caused death.

10.3.1.3. Definition of Unexpected AE or Unexpected Suspected Adverse Reaction

An AE or suspected adverse reaction is considered “unexpected”:

- If it is not listed in the IB or is not listed at the specificity or severity that has been observed, or
- If an IB is not required or available, is not consistent with the risk information described in the general investigational plan or elsewhere in the current application, as amended

For example, under this definition, hepatic necrosis would be unexpected (by virtue of greater severity) if the IB referred only to elevated hepatic enzymes or hepatitis. Similarly, cerebral thromboembolism and cerebral vasculitis would be unexpected (by virtue of greater specificity) if the IB listed only cerebral vascular accidents.

“Unexpected,” as used in this definition, also refers to AEs or suspected adverse reactions that are mentioned in the IB as occurring with a class of drugs or as anticipated from the pharmacological properties of the drug but are not specifically mentioned as occurring with the particular drug under investigation.

